- Obtaining details of concomitant medications and adverse events
- Performing complete physical examination (including retinal examination)
- Obtaining vital signs
- Obtaining body weight and height
- Obtaining blood samples for the tests listed in Table 3
- Obtaining urine sample for β -hCG pregnancy test for females of childbearing potential only
- Chart review of YRG-JHU ICC data to document HIV and antiretroviral therapy status and engagement in opioid substitution therapy (OST)

Subjects who meet all of the inclusion criteria and none of the exclusion criteria will return to the clinic for the Baseline/Day 1 visit assessments and randomization.

4a4. Randomization

A random treatment allocation list will be prepared by a staff member who is not involved in the study using a commercial statistical software package. Blocked randomization will be performed using blocks of randomly

varying sizes of 3, 6 and 9 at a 1:1:1 allocation ratio between the three arms. Blocked randomization will ensure equal distribution of participants between the three arms even if the targeted recruitment numbers are not met. Further, using a variation in the block sizes will minimize the possibility of the study staff being able to identify which arm the next subject would be allocated to. Treatment assignments will be transferred to numbered, opaque, sealed study envelopes by a staff member who is not involved with the study. Envelopes will be opened sequentially by the study physician or research manager as subjects are enrolled. Biometric information (fingerprint data) of the study participant will be recorded prior to randomization assignment.

4a5. Treatment Assessments

4a5.1. Baseline / Day 1 Visit

The following procedures will be completed prior to randomization and dosing/dispensing.

- Perform targeted physical examination
- Obtain vital signs
- Obtain body weight
- Assessment of adverse events and concomitant medications
- Pregnancy prevention counseling for female participants of childbearing potential
- Obtain blood samples for tests listed in Table 3
- Obtain urine sample for β -hCG pregnancy test for females of childbearing potential only
- Collect data from surveys including information on substance use and quality of life
- Adherence counseling
- Chart review of YRG-JHU ICC data to document HIV and antiretroviral therapy status and engagement in opioid substitution therapy (OST)

4a5.2. Treatment administration

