Moderate	Decrease PEG dose 50%	Evaluate once weekly by clinician at visit and daily recording of symptoms by outreach worker in field	Consider psychiatric consultation. Continue reduced dosing.	If symptoms improve and are stable for 4 weeks, may resume normal visit schedule. Continue reduced dosing or return to normal dose.	(See severe depression)
Severe	Discontinue PEG permanently	Immediate psychiatric consult with CIMS	Psychiatric therapy as necessary as supervised by physician at CIMS		

Table 2. Procedures for Dose modification for serious adverse events related to hematologic abnormalities

Laboratory values		Pegylated Interferon $\alpha 2a$
Hgb	<10.0 g/ dl	---
	<8.5 g/dl	Permanently discontinue
WBC	<1.5 x 10 ⁹ /L	Reduce dose by 50%
	<1.0 x 10 ⁹ /L	Permanently discontinue
Neutrophil	<0.75 x 10 ⁹ /L	Reduce dose by 50%
	<0.5 x 10 ⁹ /L	Permanently discontinue
Platelets	<50 x 10 ⁹ /L	Reduce dose by 50%
	<25 x 10 ⁹ /L	Permanently discontinue
Bilirubin – direct	2.5 x ULN*	Permanently discontinue
Bilirubin – indirect	>5 mg/dl	
	>4 mg/dl (for 4 weeks)	Permanently discontinue
Creatinine	> 2 mg/dl	Permanently discontinue
ALT/AST	2 x baseline and 10 x ULN	Permanently discontinue

*ULN = upper limit of normal

Treatment interruption

We will track missed doses using our biometric system in Arms 1 and 2. Participants who miss ≥ 1 but fewer than 2 weeks of doses will have their treatment extended so that they complete the total number of doses in their assigned arm (e.g., 28 for Arm 1 and 84 for Arm 2). If a client misses 2 weeks or more of therapy,

treatment will be restarted in its entirety at the discretion of the study physician and in consultation with the participant. Treatment can only be restarted one time. If there is a second interruption of >2 weeks, treatment will not be restarted. Participants in Arm 3 will be counseled to complete all doses of medications even if it takes longer than 84 days (e.g., 94 days). If participants in Arm 3 report an interruption >2 weeks at their 4-weekly medication refill visit, they will also be provided with one opportunity to restart treatment for the entire duration of 12 weeks at the discretion of the study clinician as with Arms 1 and 2.

4a5.3. End of Treatment Visit

The following procedures/assessments will be completed at the End of Treatment Visit

- Obtain vital signs
- Assessment of adverse events and concomitant medications

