- Review medication compliance with subject. Subject should bring any missed doses to this visit.
- Obtain blood samples for sample storage in Table 3
- Brief survey on quality of life and alcohol and drug use
- Perform targeted physical examination
- Chart review of YRG-JHU ICC data to document HIV and antiretroviral therapy status and engagement in opioid substitution therapy (OST)

4a5.4. Early termination visit

Subjects discontinuing treatment prior to completion of the assigned dosing period will be asked to complete an Early Termination visit as described below. In addition, these subjects will be asked to complete the 12-week Post Treatment visit. Subjects with HCV RNA < lower limit of quantification (LLOQ) who permanently discontinue all study drugs for any reason including safety and/or tolerability concerns prior to completion of the assigned dosing period will be followed according to the post-treatment study assessments to determine whether the subject achieves SVR.

The Principal Investigator will be consulted prior to subject discontinuation when medically feasible. Study medication will be discontinued in the follow instances:

- Unacceptable toxicity, as defined in Section 8c of the protocol, or toxicity that, in the judgment of the study clinician and principal investigator, compromises the ability to continue study-specific procedures or is considered to not be in the subject's best interest
- Pregnancy in female participants
- Significant protocol violation including non-compliance with study assessments
- Subject requests to discontinue for any reason

The following procedures will be performed at the early termination visit.

- Perform targeted physical examination
- Obtain vital signs
- Obtain body weight
- Assessment of adverse events and concomitant medications
- Obtain blood samples for:
 - HCV RNA testing
 - Complete blood count
 - Liver function tests
 - Renal function tests
 - These samples will be used to estimate FIB-4 (stage fibrosis)
- Brief survey on quality of life and alcohol and drug use
- Subject should return all extra medication doses at this visit
- Chart review of YRG-JHU ICC data to document HIV and antiretroviral therapy status and engagement in opioid substitution therapy (OST)

4a5.5. 12-week post-treatment visit (Week 16 for Arm 1 and Week 24 for Arms 2 and 3)

The following procedures will be performed at the 12-week post treatment visit.

- Obtain vital signs
- Obtain body weight

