Vital signs: Assessment of vital signs will include measurement of resting blood pressure, pulse, respiratory rate and temperature.

Pregnancy testing: All females of childbearing potential will have a urine pregnancy test at the Screening and Baseline visits.

Survey: We will use the EuroQOL-5D as well as the WPAI: Hepatitis C Quality of Life Surveys. These will be translated into the local language. While these surveys are intended to be self-administered, low literacy rates in our population will require that they be interviewer administered. We will also include brief questions on frequency of drug and alcohol use.

Chart Review: The YRG-JHU ICC maintains an electronic database to monitor client visits, test results and service utilization. Data that are available through this database will be abstracted from these patient records rather than collected de novo. Specifically, we are interested in HIV status and whether participants are engaged in antiretroviral therapy and/or opioid substitution therapy.

b. Study duration and number of study visits required of research participants.

Participants in all Arms will have 4 study visits (Screening, Baseline, End of Treatment and SVR12). Participants in Arm 1 will have an additional 3 visits for interferon injections, and participants in Arm 3 will have an additional two visits to pick up medication refills. The duration of the study will be 16 weeks for Arm 1 and 24 weeks for Arms 2 and 3.

c. Blinding, including justification for blinding or not blinding the trial, if applicable.

This study will not be blinded. In part, this is so that clinicians can appropriately monitor for side effects associated with pegylated interferon alfa-2a. The regimens delivered require different forms of delivery (e.g., pegylated interferon is an injectable medicine) and for different durations of time making blinding not feasible.

d. Justification of why participants will not receive routine care or will have current therapy stopped.

All participants will be able to receive the same routine medical care that they receive at the center and no other therapies will be stopped.

e. Justification for inclusion of a placebo or non-treatment group.

This study does not involve a placebo group.

f. Definition of treatment failure or participant removal criteria.

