5. If participant is co-infected with HIV, he/she must have a CD4 $>$ 350 cells/mm³ and be either: 1) ART naïve or 2) on ART be on a tenofovir-containing regimen. If a subject's CD4 drops below 350 cells/ μ L (current threshold for HIV treatment in India), he/she will be able to initiate ART but we will ensure that the subject starts on a tenofovir-containing regimen, which is currently the standard for persons newly initiating ART in India.
6. Subjects must have the following laboratory parameters at screening:
 - a. ALT \leq 10 x the upper limit of normal (ULN)
 - b. AST \leq 10 x ULN
 - c. Hemoglobin \geq 10 g/dl for male and 9 g/dl for female subjects
 - d. International normalized ratio (INR) \leq 1.5 x ULN unless subject has known hemophilia or is stable on an anticoagulant regimen affecting INR
 - e. Albumin \geq 3 g/dl
 - f. Direct bilirubin \leq 1.5 x ULN
 - g. Creatinine clearance \geq 30 ml/min as calculated by the Cockcroft-Gault Equation
 - h. Alpha fetoprotein $<$ 50 ng/ml
 - i. Absolute neutrophil count (ANC) \geq 1,500/ μ L
 - j. Platelets \geq 90,000/ μ L
 - k. Thyroid stimulating hormone (TSH) \leq ULN
 - l. FIB-4 \leq 3.25 (Participants with a FIB-4 $>$ 3.25 will be referred to the medical gastroenterology department for further assessment for cirrhosis. If further assessment rules out cirrhosis participants can be rescreened for the study.)
7. A female subject is eligible to enroll in the study if it is confirmed that she is:
 - a. Not pregnant or nursing
 - b. Not of childbearing potential (i.e., women who have had a hysterectomy, have both ovaries removed or medically documented ovarian failure, or are postmenopausal women $>$ 50 years of age with cessation (for \geq 12 months) of previously occurring menses)
 - c. Of childbearing potential (i.e., women who have not had a hysterectomy, both ovaries removed or medically documented ovarian failure). [NOTE: Women \leq 50 years of age with amenorrhea will be considered to be of childbearing potential.] These women must have a negative urine pregnancy test at screening and a negative urine pregnancy test on the Baseline /Day 1 visit prior to randomization and agree to one of the following modes of contraception for the duration of treatment and 12 weeks thereafter.
 - Complete abstinence from intercourse. Periodic abstinence (e.g., calendar, ovulation, symptothermal, post-ovulation methods) is NOT permitted.

or

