- i. Consistent and correct use of 1 of the following methods of birth control listed below in addition to a male partner who correctly uses a condom from 3 weeks prior to Baseline/Day 1 until the end of treatment. Women of childbearing potential must not rely on hormone-containing contraceptives as a form of birth control during the study. Female subjects using a hormone containing contraceptive prior to screening may continue their contraceptive regimen in addition to the study specified methods of birth control.

- intrauterine device (IUD) with a documented failure rate of less than 1% per year
- female barrier method: cervical cap or diaphragm with spermicidal agent
- tubal sterilization
- vasectomy in male partner

8. Subjects must be of generally good health as determined by the investigator.
9. Subjects must be able to comply with the dosing instructions for study drug administration and be willing to complete the study schedule of assessments.

Exclusion criteria: Subjects who meet *any* of the following exclusion criteria will not be enrolled in the study.

1. Pregnant or nursing female
2. Current or prior history of clinical hepatic decompensation (e.g., ascites, encephalopathy or variceal hemorrhage, MELD<12)
3. Prior treatment for hepatitis C virus infection
4. Infection with hepatitis B virus (HBsAg positive)
5. Chronic use of systematically administered immunosuppressive agents (e.g., prednisone equivalent >10 mg/day)
6. Use of any prohibited concomitant medications within 28 days of the Baseline/Day 1 visit.
7. Contraindications to PEG
8. Known hypersensitivity to the metabolites or formulation excipients of PEG (for Arm 1 subjects)
9. Active significant psychiatric condition(s) including severe depression, severe bipolar disorder and schizophrenia. Other psychiatric disorders are permitted if the condition is well controlled with a stable treatment regimen for ≥ 1 year from screening, or inactive for ≥ 1 year from screening.
10. Presence of autoimmune disorders (e.g., systemic lupus erythematosus, rheumatoid arthritis, sarcoidosis, psoriasis of greater than mild severity)
11. History of clinical significant retinal disease
12. Clinical evidence of cirrhosis

6. Drugs/ Substances/ Devices

a. The rationale for choosing the drug and dose or for choosing the device to be used.

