years and has extensive experience in delivering HIV care. They will receive training from physicians at the Johns Hopkins Viral Hepatitis Clinic who have been treating hepatitis C for 20 years and the team at YRGCARE in Chennai who have been treating HCV for the past 5 years. They will be trained to look for and manage all potential adverse effects of therapy and will have the ability to receive guidance from experts from the Johns Hopkins Viral Hepatitis Clinic ([name]). Through Centers for Disease Control funding, a new Maryland Community-Based Program To Test and Cure Hepatitis C has been established. Administered by the Maryland Department of Health and Mental Hygiene (DHMH) in collaboration with a coalition of clinical and public health partners, this initiative will strengthen healthcare capacity to diagnose and cure HCV infection through the implementation of a clinician training and on-going telemedicine program. The clinician training and telemedicine program will be implemented by the Division of Infectious Diseases at Johns Hopkins University (JHU), a national leader in viral hepatitis management. Through its Viral Hepatitis Center (VHC), JHU will train clinicians to effectively test for HCV and offer appropriate treatment. As part of this training program, clinicians at our site in India will have access to weekly video conferences, which include provider clinical case consultations and co-management of cases as well as on call- 24 hour clinical consultations.

Female participants will be guided to exercise care to avoid pregnancy in female subjects. Women of childbearing potential will be required to use effective methods of birth control. The study doctor will document what type(s) of birth control are being used. Participants will be given strict instructions about what to do if they become pregnant during the course of the study.

Finally, field workers will be trained to exercise discretion when delivering SOF and DAC in the field. The daily meeting will occur at a place, which the participant chooses and the field worker will not identify as being a part of a study nor with anything related to injection drug use or hepatitis C. Most of the field workers employed are former drug users and hence, have an excellent rapport with the study community and have experience in reaching PWID in the field as part of the YRG-JHU ICC study.

c. Plan for reporting unanticipated problems or study deviations.

8c1. Adverse Events (AE)

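### Pregnancy must stop study drug, but no pregnancy test is scheduled after Day 1 and none is required before a full treatment restart (low-priority safety improvement)

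*Combined protocol and SAP*

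**What the plan says.** Section 4a5.4 lists "Pregnancy in female participants" among the reasons to discontinue study medication.

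Testing is set out in three places that agree. Section 4a5.6 states "All females of childbearing potential will have a urine pregnancy test at the Screening and Baseline visits". The Screening and Baseline procedure lists (4a3, 4a5.1) each include a urine test. Inclusion criterion 7c also requires a negative screening test and "a negative urine pregnancy test on the Baseline /Day 1 visit prior to randomization". No pregnancy test appears in Table 3, in the End of Treatment, Early Termination or 12-week post-treatment lists, or in the descriptions of the Arm 1 injection visits and Arm 3 refill visits.

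On restarts, section 4a5.2 says that after two weeks or more of missed therapy "treatment will be restarted in its entirety at the discretion of the study physician and in consultation with the participant". For Arm 3 participants who report an interruption of more than two weeks, "they will also be provided with one opportunity to restart treatment for the entire duration of 12 weeks", again at the clinician's discretion. Neither rule names a pregnancy test.

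The plan does have safeguards:
- Criterion 7c requires contraception during treatment and for 12 weeks after it.
- The Day 1 visit includes "Pregnancy prevention counseling for female participants of childbearing potential".
- Section 8b states "The study doctor will document what type(s) of birth control are being used" and promises participants instructions on what to do if they become pregnant.
- Section 8b also provides phone and SMS contact, weekly monitoring in Arm 1 and daily field monitoring in Arms 1 and 2.

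**The concern.** The stop rule works only if someone knows about the pregnancy. After Day 1 that depends on the participant or a clinician suspecting it. Two features of the plan weaken that signal. Women aged 50 or under with amenorrhea are classed as of childbearing potential, and for them a missed period tells nothing. Nausea and fatigue are listed in section 7b as common interferon effects, so in Arm 1 early symptoms could be put down to the drug. Arm 3 has the least staff contact: between Day 1 and End of Treatment it is seen only at Weeks 4 and 8, when a further 28 days of drug are handed over untested.

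The restart is the clearest gap. The plan requires a negative test before the first course but not before a second full course, which may begin weeks or months after the last test. A woman who conceived early and did not recognise it could stay on drug, or start a whole new course, although the plan says drug must stop.

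**Working it through.** The plan gives no figure on this point, so there is none to reproduce. The steps below size the untested period, the expected number of cases and the gain from testing.

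**1. Time since the last scheduled test (4a5.2)**
- Planned dosing after Day 1: 28 days in Arm 1, 84 in Arms 2 and 3. Scheduled tests in that time: 0.
- With one restart after an assumed 14-day gap, elapsed days from Day 1 to the last dose are at least 1 + 14 + 28 = 43 (Arm 1) or 1 + 14 + 84 = 99 (Arms 2 and 3). They are at most about 27 + 14 + 28 = 69 or 83 + 14 + 84 = 181. A longer gap adds to these.
- Mid-course illustration: dosing days are 14 + 28 = 42 or 42 + 84 = 126, over 56 or 140 elapsed days.

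**2. Expected on-treatment conceptions**
- Women of childbearing potential: not stated. Assumed 5 to 20% of 150 = 7.5 to 30, about 8 to 30.
- Conception rate: assumed 1 to 10% per year. The low end borrows the plan's only contraceptive failure figure, "intrauterine device (IUD) with a documented failure rate of less than 1% per year"; the high end has no source in the documents.
- Mean planned treatment: (4 + 12 + 12)/3 = 9.33 weeks = 0.179 years.
- Low: 7.5 × 0.179 × 0.01 = 0.013. High: 30 × 0.179 × 0.10 = 0.54.

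**3. Gain in Arm 3 from tests at Days 28 and 56**

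Assume that the test turns positive 14 days after conception, that conception is uniform over 84 days, and that nobody recognises the pregnancy unaided.
- No tests: mean dosing after conception = 84/2 = 42 days; longest 84.
- Conception on Days 0 to 14: found at Day 28; mean 21 days.
- Conception on Days 14 to 42: found at Day 56; mean 28 days.
- Conception on Days 42 to 84: not found before dosing ends; mean 21 days.
- Mean with tests: (14 × 21 + 28 × 28 + 42 × 21)/84 = 1960/84 = 23.3 days; longest 42.
- Saving per conception: 42 − 23.3 = 18.7 days.
- Expected Arm 3 conceptions: 2.5 to 10 women × 0.01 to 0.10 × 84/365 = 0.006 to 0.23. The expected saving is about 0.1 to 4.3 dosing days over the whole arm.

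**4. Gain in Arm 1 from a Week 3 test**

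With the same lag, a Day 21 test finds only conceptions in Days 0 to 7 and saves 28 − 21 = 7 days each. Mean saving: 7 × 7/28 = 1.75 days per conception.

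**5. Gain from a pre-restart test**

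The gap is about 14 days or more. With a 14-day lag, a test at restart is therefore positive for any conception before the interruption began. Each such finding avoids a full further course: 28 dosing days in Arm 1, 84 in Arms 2 and 3. The restart frequency is not stated, so no expected total can be given.

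**The case against.** The case against acting is reasonable. Women are tested twice before dosing, must use contraception through treatment and for 12 weeks after (which on its wording also covers a restarted course), are counselled, and can reach staff by phone or SMS in every arm. A restart is not automatic: it needs clinician judgement, happens once at most, and leaves the stop rule in force. The most likely number of affected participants is zero. The documents give no fetal risk figure, so the harm per exposure is unknown. How often to repeat a test in a 4- or 12-week course is partly a matter of preference. All of this stands, and it is why the priority is low. It does not remove the gap, because none of these measures tests for pregnancy.

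Three stronger readings are tempting but not supported:
- A reader might infer that the protocol contradicts itself. It does not. Section 4a5.4 says what to do if pregnancy occurs; it does not promise active screening.
- A reader might infer that pregnancies would not be followed to birth. Sections 8c1 and 8c2 exclude uncomplicated pregnancy from adverse events yet count a birth defect as serious, and no follow-up to delivery is described in the sections available. But the consent pages were removed before review, and the instructions promised in 8b may cover it. Complications and terminations are already adverse events with follow-up. This is a query to the sponsor, not a finding.
- A reader might take the fall from 84 to 42 days in Arm 3 as the typical gain. Those are the longest cases; the means are 42 and about 23 days.

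**Conclusion.** The point holds as a low-priority safety improvement. On the text, no pregnancy test is scheduled after Day 1 and none is a condition of a full restart in any arm. Followed as written, the plan permits untested re-dosing and untested dispensing to women for whom pregnancy must stop drug.

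The size is small: about 0.01 to 0.5 expected on-treatment conceptions, resting on an assumed number of women and an assumed conception rate. The Arm 3 gain of about 19 dosing days per conception also rests on the 14-day lag and on no self-recognition; some self-recognition would shrink it. Scheduled on-treatment testing would do little in Arm 1. Arm 2 has no clinic visit during dosing, so the required changes give it no on-treatment detection except before a restart. The SVR12 comparison and the sample size are not affected.

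**What to change.** 1. In 4a5.2, require a negative urine pregnancy test for women of childbearing potential before any treatment restart, in all arms. In Arm 3 the test at the refill visit can serve.
2. In 4a5.6 and Table 3, add a urine test before dispensing at the existing Arm 3 Week 4 and Week 8 visits, and at End of Treatment or Early Termination in all arms. The End of Treatment test cannot trigger the stop rule and can miss conceptions in about the last two weeks of dosing; its use is to identify exposed pregnancies.
3. Optional: a Week 3 test in Arm 1 before the fourth injection, and a roughly monthly private test at the integrated care centre (ICC) for Arm 2.
4. Ask the sponsor whether the consent form or participant instructions provide for following an uncomplicated pregnancy to birth.

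Cost of items 1 and 2: one kit per woman in Arms 1 and 2 and three in Arm 3, a mean of (1 + 1 + 3)/3 = 1.67. That is about 13 kits for 8 women or 50 for 30, plus one per restart where no scheduled test serves. The scheduled tests fall at existing visits; a pre-restart test may need an extra one. With both optional additions the mean is (2 + 3 + 3)/3 = 2.67, or about 21 to 80 kits. The Arm 2 option adds up to two ICC visits per woman; if paid INR 100 each, as Arm 1 injection visits are, that is 2.5 to 10 women × 2 × 100 = INR 500 to 2,000.
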